# Statistical Analysis Plan

**Name of Study: Memory and Fear Study (Fear of Memory Loss Study)**

**NCT Number: NCT04821960**

**Version Date: 22 June 2022**

## Study Information

### Research questions

1. What is the efficacy of a 3-week mindfulness and behavioral activation program to reduce fear and avoidance of memory loss in community-dwelling older adults? We predict a reduction in fear and avoidance of memory loss across weeks. We also predict that participants who receive psychoeducation, mindfulness and behavioral activation training (experimental group) will exhibit a greater reduction in fear and avoidance than those who receive psychoeducation and mindfulness only (active control group).
2. What is the efficacy of a 3-week mindfulness-based program to reduce fear of dementia and improve psychosocial functioning in community-dwelling older adults? We predict that fear of dementia will decrease and psychosocial functioning will increase (mood, quality of life, social engagement and self-rated memory) across weeks.

### Hypotheses

1. Fear and avoidance of memory loss will be lower at follow-up compared to baseline. Fear and avoidance scores will be lower in the experimental group than the active control group.
2. Fear of dementia, anxiety and self-reported memory failures will be lower at follow-up compared to baseline. Quality of life and social engagement will be higher at follow-up compared to baseline.

## Data Description

### Datasets used

Reducing Fear and Avoidance of Memory Loss (REFRAME) Study scores (PIs: [name], [name] and [name]).

### Data availability

Data will be fully anonymised and will be made available on [clinicaltrials.gov](https://clinicaltrials.gov).

### Data access

The data are not public and are accessible by the study team only.

**Data identifiers**

No response

**Access date**

Data will be made available as soon as they are collected and checked.

**Data collection procedures**

Participants are 80 cognitively healthy adults aged 55 years and older residing anywhere in the United States with elevated fear and avoidance of memory loss ( $\geq 61$  total score on the Fear and Avoidance of Memory Loss scale). Exclusion criteria were diagnosis of neurodegenerative condition (e.g., Alzheimer's disease), impaired cognitive function ( $< 18$  score on the Montreal Cognitive Assessment), unstable medical condition, severe depression ( $\geq 12$  score on the Geriatric Depression Scale), current participation in psychotherapy, current substance use disorder and inadequate vision or hearing to interact with study material.

Eligibility was determined by an online screening questionnaire followed by an additional phone screener. Eligible participants were randomly assigned to experimental or active control groups. Both groups completed questionnaires (pre-intervention, post-intervention and 4-week follow-up) and three weeks of self-administered program materials. The experimental group completed psychoeducation, mindfulness and behavioral activation exercises. The active control group completed psychoeducation and mindfulness only. All data was collected and stored on REDCap.

**Codebook**

The codebook is attached.

**Variables****Manipulated variables**

No response

**Measured variables**Primary outcome measure:

Fear and Avoidance of Memory Loss (FAM) scale. 23-item scale with scores between 23-115. Higher scores indicate higher fear and avoidance of memory loss.

Secondary outcome measures:

Fear of Alzheimer's Disease Scale (FADS). A 30-item scale with scores between 0-120. Higher scores indicate higher fear of developing Alzheimer's disease.

Patient Reported Outcome Measures Information System-29 (PROMIS-29) quality of life, social functioning and anxiety subscales, measured in T score units. Higher scores indicate higher quality of life, social functioning and anxiety, respectively.

World Health Organisation Well-Being Index (WHO-5). 5-item scale assessing overall well-being with scores between 0-25. Higher scores indicate higher well-being.

Memory Failure Scale (MFS). 12-item scale with scores between 12-60. Higher scores indicate more frequent reported memory lapses.

### **Unit of analysis**

No response

### **Missing data**

No response

### **Statistical outliers**

No outliers will be dropped from analyses, but all variables will be inspected for the shape of distributions and potential univariate outliers.

### **Sampling weights**

No response

## **Knowledge of Data**

### **Prior Publication/Dissemination**

The protocol for the study was published in 2021 (O'Loughlin et al, 2021).

### **Prior knowledge**

We looked at preliminary data from eight participants (FAM scores only) before the data analysis plan was finalised. No changes were made to the analysis plan after viewing these data. \*

## **Analyses**

### **Statistical models**

#### Primary analysis:

Fear and Avoidance of Memory Loss (FAM) will be used as the dependent variable. In a mixed model, Time (T) and time-by-program group (Tx) interaction terms will be independent variables, for each time point after baseline where treatment is expected to have an effect. This is consistent with a response profile analyses (Fitzmaurice, G., Davidian, M., Verbeke, G., & Molenberghs, G. (Eds.). (2008). Longitudinal data analysis, CRC press). To test the effect of treatment, the full model will be compared to a reduced model where all effects including treatment are removed from the model.

Full model:

$$\text{FAM} = \text{T1 (baseline)} + \text{T2 (week 1)} + \text{T3 (week 2)} + \text{T4 (week 3)} + \text{T5 (follow-up)} + \text{T2:Tx} + \text{T3:Tx} + \text{T4:Tx} + \text{T5:Tx}$$

Reduced model:

$$\text{FAM} = \text{T1 (baseline)} + \text{T2 (week 1)} + \text{T3 (week 2)} + \text{T4 (week 3)} + \text{T5 (follow-up)}$$

The full and reduced models (estimated using ML) will be compared to test the significance of all terms involving treatment. Reduced models comparing post-treatment to baseline within group will test the effect of time.

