Interventions that disrupt these vicious cognitive-behavioral cycles could afford immediate improvements in dementia-related fears and mental health, as well as long-term benefits (e.g. curtailing cognitive decline [6]). Crucially, mindfulness-based interventions have been shown to improve health and well-being outcomes in other conditions, such as chronic pain and fatigue, by improving individuals' ability to acknowledge negative thoughts and feelings without fixating on them [7-9]. However, few studies have investigated the use of mindfulness-based interventions in the context of dementia-related fear. In addition, extant interventions are often modified from pre-existing psychological interventions (e.g. mindfulness-based cognitive therapy). These approaches therefore require a high level of support and specialist training to administer. In addition, they lack relevance for older adults experiencing sub-clinical levels of dementia-related anxiety, who may be at risk for dementia. To address these limitations, we will use newly developed web-based technology to deliver a low-intensity intervention to help older people manage dementia-related fears in daily life.

We will develop a web-based mindfulness plus activation intervention tailored to mitigate dementia-related fears and improve well-being in a sample of older adults experiencing heightened dementia-related fear. This three-week program will focus on (1) mindfulness-based exercises to identify and monitor dementia-related fears and (2) behavioral-based exercises to overcome maladaptive fear avoidance (FA-mindfulness). An active control group will receive a typical meditation intervention. Therefore, this project will (1) determine the impact of the FA-mindfulness on dementia-related fear and maladaptive avoidance, (2) maximize convenience by developing a web-based intervention program and (3) investigate a low-cost approach to promote health-related outcomes in older adults.

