The intervention will consist of three weeks’ worth of sessions of mindfulness and de-centering exercises (and behavioral activation exercises for the experimental group). Each week of the intervention, participants will be asked to complete mindfulness activities 4 days of the week. These activities will take about 10-30 minutes to complete each day that an activity is assigned. Each week of the intervention will focus on psychoeducation and mindfulness lessons. Week 1 will consist of psychoeducation on memory loss, dementia, fear of dementia, and general health anxiety. Participants will also complete a beginner’s mindfulness technique towards the end of the week. Week 2 will consist of psychoeducation about mindfulness and meditation. Participants will learn about and practice mindfulness techniques throughout the week. They will also complete written activities. During week 3, participants in the control group will continue practicing and using mindfulness techniques taught in week 2 of the intervention. The experimental group will learn about behavioral activation strategies and practice activities related to behavioral activation throughout the week. After completing each week’s activities, participants will complete a short set of questionnaires. We expect that modules for the control and experimental groups to take about the same amount of time to complete. We estimate about 10-30 minutes each day that an activity is assigned because similar amount of audio files and activities are provided to each group.

All modules of the mindfulness intervention will be completed within REDCap forms designed based on the intervention materials developed with this protocol. The modules will consist of audio files, exercises (e.g., multiple choice questions, writing activities, meditation exercises, etc.), and summarization of concepts learned in each module. Each week of the intervention, participants will be emailed with that week’s links to the assigned intervention modules. The links will be sent in the beginning of the week to the participant’s specified email address. For each of the 3 weeks of the intervention, the participant will complete four modules that will each take between 10-

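### The primary model's five FAM levels are not mapped to the six scheduled FAM visits, and which visit serves as baseline can decide whether the arm estimates are unbiased or halved

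*SAP*

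**What the plan says.** **Model.** The SAP (Statistical models, Primary analysis) fits FAM on five levels, T1 to T5, labelled baseline, weeks 1 to 3 and follow-up. Arm terms enter at T2 to T5, "for each time point after baseline where treatment is expected to have an effect". There is no arm term at T1, so both arms share one baseline mean. Full and reduced models are "compared to test the significance of all terms involving treatment". Separately, "Reduced models comparing post-treatment to baseline within group will test the effect of time". No level is labelled post-treatment.

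**Schedule.** Protocol Table 1 marks FAM at six visits: two weeks pre-intervention, sessions 1, 2 and 3, post-intervention (one week after session 3), and follow-up. The payment table in Section 14.0 also has six rows. The SAP power statement (Effect size) uses six repeated measures. Protocol Sections 1.0 and 8.0 say five time points. SAP Data collection procedures names three occasions: "Both groups completed questionnaires (pre-intervention, post-intervention and 4-week follow-up".

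**Baseline.** Section 8.0 places the baseline visit two weeks before the intervention, whereas Table 1 attaches the word to session 1. Section 4.0 puts randomization before the modules are sent. Section 8.0 puts intervention-week questionnaires after that week's materials, with the expectation item as the only exception.

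**Content.** Section 8.0 first describes an arm difference in week 3: "The experimental group will learn about behavioral activation strategies and practice activities related to behavioral activation throughout the week". Its opening sentence mentions such exercises without naming a week ("and behavioral activation exercises for the experimental group"), and Section 1.0 says "An active control group will receive a typical meditation intervention". The SAP says "The active control group completed psychoeducation and mindfulness only".

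**The concern.** A model with a common baseline mean is sound when T1 precedes anything that could separate the arms. If T1 comes after randomization and a week of materials, any arm difference already present is treated as chance imbalance, and part of it is subtracted from every later estimate. Participants know their assignment (Section 8.0), so an early difference cannot be excluded even if the content is the same.

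The five-level model must also leave out one scheduled FAM, and the SAP does not say which. Depending on the answer, the unused score is either the post-intervention FAM or the two-weeks-pre FAM, which is the only one that precedes all content under every reading. These are different analyses of the primary outcome, and nothing in the SAP fixes the choice before the data are seen.

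**Working it through.** **1. The SAP's own power figures.** Inputs from Effect size and Statistical power: f = 0.25, alpha 0.05, two groups, correlation 0.5. For the G*Power within-between interaction, lambda = f² × N × m × epsilon / (1 − rho), with df (m − 1)epsilon and (N − 2)(m − 1)epsilon.

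- m = 6, N = 80, epsilon 1: lambda = 0.0625 × 80 × 6 / 0.5 = 60; df 5 and 390; power above 99.9% (stated 99%).
- m = 6, N = 40, epsilon 0.5: lambda = 0.0625 × 40 × 6 × 0.5 / 0.5 = 15; df 2.5 and 95; power 92.1% (stated 92%). The SAP's 40 is therefore the total; N = 80 with epsilon 0.5 gives 99.9%.
- m = 5, N = 40, epsilon 0.5: lambda = 12.5; df 2 and 76; power **88.4%**.
- m = 5, N = 80, epsilon 1: lambda = 50; power above 99.9%.

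**2. Readings of T1 to T5.**

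| Reading | T1 | T2, T3, T4 | T5 | FAM not used |
|---|---|---|---|---|
| A | two weeks pre | sessions 1, 2, 3 | follow-up | post-intervention |
| B | session 1, after week 1 materials | sessions 2, 3, post-intervention | follow-up | two weeks pre |
| C | session 1, before any content | sessions 2, 3, post-intervention | follow-up | two weeks pre |

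A agrees with the Section 8.0 text and the payment labels. B combines Table 1's label with the Section 8.0 timing rule. C fits Table 1's label and the SAP's week labels but conflicts with that rule.

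**3. What the choice does.** Assumptions, not in the documents: 40 per arm, no dropout, effects in FAM SDs, and correlation either equal at 0.5 (CS) or AR(1) 0.7 by position in the six-visit schedule. The protocol uses d = 0.4 for sample size only.

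With a common T1 mean, the expected estimate at visit j is d_j − rho_j1 × d_1, and the estimates have covariance (2/n) × Cov(later visits given T1). Under CS 0.5 that conditional covariance is 0.5 × I + 0.25 × J, where J is the all-ones matrix. For an equal estimate e at k later visits, lambda = (n/2) × e² × k / (0.5 + 0.25k).

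For a 0.4 SD difference sustained from session 1:

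- Reading A: d_1 = 0, so e = 0.4. Lambda = 20 × 0.16 × 4 / 1.5 = 8.53 on 4 df; power **64%**, unbiased.
- Reading B: d_1 = 0.4, so e = 0.4 − 0.5 × 0.4 = 0.20. Lambda = 20 × 0.04 × 4 / 1.5 = 2.13; power **18%**, estimates halved.
- Reading C: the difference starts after T1, so e = 0.4; power 64%, unbiased.
- All six visits, two-weeks-pre first: lambda = 20 × 0.16 × 5 / 1.75 = 9.14 on 5 df; power 63%, unbiased.

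Under AR(1) 0.7 the powers are 63.5% (A), 19% (B), 60% (C) and 60% (six visits). Reading B's expected estimates are 0.4 × (1 − 0.7^s) for s = 1 to 4, that is 0.12, 0.20, 0.26 and 0.30. A likelihood-ratio simulation under CS 0.5 (800 runs per cell) gave 62.5% for A and 16.5% for B.

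**4. What the joint test shows.** Under reading A with CS 0.5, a 0.4 SD difference only at sessions 1 and 2 rejects 64% of the time, exactly as often as one only at session 3 and follow-up. Rejection does not say when the arms differed.

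**5. Whether a late-visit test would isolate behavioral activation.** In the six-visit model, take the 5-df joint test followed by a 3-df test of session 3, post-intervention and follow-up (400,000 draws). Both are significant this often:

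| True 0.4 SD difference | CS 0.5 | AR(1) 0.7 |
|---|---|---|
| Late visits only | 59% | 37% |
| Sustained from session 1 | 56% | 39% |
| Sessions 1 and 2 only | 4.9% | 4.9% |

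The sequence screens out an early difference that vanishes, but not one that persists.

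**The case against.** **Reading B is strained, so its 18% should not be taken as the expected result.** This stands in part. Under B with the Section 8.0 timing rule, the level labelled week 1 is collected after the week 2 materials, which contradicts the SAP's label. C avoids that and is unbiased, but only by setting the timing rule aside. The documents do not settle the matter. The 18% shows what is at stake if B is fitted; it does not predict what will be.

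**Under A, the within-group test still has a visit to use.** This stands. By the timing rule the session 3 FAM follows all materials and can serve as post-treatment. The loss under A is the unused post-intervention score.

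**A mapping may exist elsewhere.** This is possible. The SAP refers to an attached codebook and a published protocol, neither of which was supplied. The SAP should still state the mapping.

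**Behavioral activation starts in week 3, so a joint test that includes weeks 1 and 2 might seem invalid or unable to answer the hypothesis.** A reader might infer this, but the documents do not support it. The SAP's Research questions and Hypotheses predict that the experimental arm does better than control. That is a randomized comparison of two programs, with no visit named. A joint test of all post-baseline arm terms answers it, and the choice of visits does not inflate type I error under the global null. The clause about expected effects can simply mean every post-baseline visit. Nor do the documents say that weeks 1 and 2 are identical; the opening sentence on content in Section 8.0 and the comparator in Section 1.0 leave early differences possible.

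**Conclusion.** The gap is real and should be fixed before the model is fitted. The SAP models five FAM levels, schedule and power statement have six, and baseline has two meanings. For a 0.4 SD difference sustained from session 1, the result is 64% power without bias if T1 is the two-weeks-pre visit. It is 18% with estimates of 0.20 SD if T1 is session 1 after the week 1 materials. Under AR(1) 0.7 the powers are 63.5% and 19%. These figures rest on the assumed effect, correlations, 40 per arm and no dropout. If session 1 precedes all content there is no bias, and power for a difference from week 1 on is 64% (CS) or 60% (AR(1)).

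The effect on the power statement is small: 92% becomes 88.4% with five measures, and the 99% figure stands.

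Two stronger conclusions do not follow. The joint test is not invalid; it only leaves the timing of any difference open. And a late-visit test would not establish that behavioral activation caused the difference, because one already present at session 1 passes it about as often.

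**What to change.** 1. State which Table 1 visit each model level is. Reconcile the two uses of baseline and the questionnaire timing rule in Section 8.0. Model all six scheduled FAM visits, with the two-weeks-pre score as the common-mean baseline, and say whether that score is the eligibility FAM (61 or higher).
2. Keep the primary test as the joint ML comparison of all arm terms, now on 5 df. Report each visit's arm difference with a 95% confidence interval.
3. Make any joint test of session 3, post-intervention and follow-up secondary. Describe it as showing only that the arms differ at those visits, and read it beside the session 1 and 2 estimates.
4. Add sex, the randomization stratum, as a fixed effect. The gain is small: standard errors fall 0.3–1.9% if sex explains an assumed 2–10% of FAM variance. Correct protocol Sections 3.0 and 8.0, which call the stratification factor age but list female and male.
5. Align the number of repeated measures in the power statement with the model. If five visits are kept, restate 92% as 88%.

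**Cost.** A dated SAP amendment; Table 1 already schedules every FAM score needed. It should disclose that FAM data from eight participants had been viewed (SAP, Prior knowledge). Compared with reading A, the sixth visit costs up to about 4 points of power under AR(1) 0.7 (for a sustained difference, 63.5% to 60%). Under CS 0.5 it raises power for a difference confined to session 3 onward from 64% to 72%.

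If the two-weeks-pre FAM is the eligibility score, arm comparisons hold but the within-group time test includes regression to the mean. As an illustration, with the cut-off 0.5 SD above the population mean and correlation 0.5, the expected fall without any treatment effect is (1 − 0.5) × 1.14 = 0.57 SD, where 1.14 SD is the mean of a normal score above that cut-off. The size depends on both assumptions, so that test should not be read as a program effect.

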#### Secondary analyses:

Similar models will be used with Fear of Alzheimer's disease (FADS), quality of life (QoL), social engagement (Soc), anxiety (Ax) and self-reported memory failures (MF) as the dependent variable, and Time (T) and program group (Tx) as independent variables.

#### **Effect size**

Power was estimated in G\*Power with the following assumptions: medium effect size ( $f$ ) = 0.25, Type I error rate = 0.05, sample size = 80, groups = 2, repeated measures = 6, correlation among repeated measures = 0.5, and nonsphericity correction epsilon = 1.0 (i.e., no correction).

#### **Statistical power**

Assumptions yielded high power (99%). We anticipated losing some participants to follow-up and investigated a nonsphericity epsilon of 0.5; power remained at 92% even with the more conservative epsilon and with  $n = 40$ . Although these power estimates are high, a goal of this study is to determine the effect sizes (within-subjects and across groups) for future randomised controlled trials.

#### **Inference criteria**

We will use a two-tailed alpha of .05 for all tests.

#### **Reliability and Robustness testing**

We will conduct regression diagnostics (e.g., inspection of residuals, multicollinearity) and conduct additional analyses as needed, such as using REML in addition to ML for model-fitting, and considering robust regression approaches.

#### **Exploratory analysis**

Exploratory analyses will include testing if (1) fear of COVID-19 (COVID-19 anxiety scale) and (2) patient beliefs about the intervention (Patient Global Impression of Change) impact its efficacy. All exploratory analyses will be labelled as such.
